Study Title: The Emmetropization Via Accommodation (EVA) Study

NCT Number: NCT03669146

Document Date: January 6, 2024

Emmetropization Via Accommodation (EVA) Study

I. Objective. The objective of this study is to determine if wearing a moderate spectacle under-correction (3.00D) and performing activities designed to stimulate accurate accommodation during a 15-month period will enhance emmetropization in highly hyperopic ($\geq +5.00D$) 3-month old infants. Our hypothesis is that more active and accurate accommodation, promoted with spectacle under-correction and accommodative exercises, will increase the rate of axial elongation to reduce hyperopia. The prediction is that the eye will modulate axial length by modifying ocular shape, that more accurate accommodation will be associated with creating a less oblate, more prolate eye shape that accentuates elongation. The results of this study would be clinically relevant almost immediately. Results from the proposed study would represent evidence-based guidelines for effective infant refractive care.

II. Background and Rationale. Most healthy human infants are born hyperopic, or farsighted (Mayer, Hansen, Moore, et al., 2001). The average cycloplegic refractive error for infants at birth ranges from +1.00D to +2.50D with standard deviations ranging from 1.50D to 2.50D (Cook and Glasscock, 1951; Luyckx, 1966; Mayer et al., 2001; Santonastaso, 1930; Wood, Hodi and Morgan, 1995; Zonis and Miller, 1974). Infants undergo a process called emmetropization in which their normal early hyperopic refractive error decreases over time by coordination of the development of optical power and axial length of the eye.

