There is no universally accepted outcome measure for infant accommodative response, therefore the analysis in this phase will be somewhat exploratory. The simplest metric to calculate would be the average accommodative response. However, variability in that response provides a useful perspective that distinguishes the infant with stable accommodation from the one that is less well-controlled or exhibits more of a searching accommodative behavior. Variability will be added as a covariate in analyses of the accommodative response. The simple standard deviation in accommodation is one measure of this variability. Another approach would be to look for periodic variability through Fourier analysis of the response. This analysis would be exploratory. Analyses are typically of 10 second segments of response. If infants are too unsteady to give such lengths of uninterrupted data, then the analysis may not be feasible. If the analysis can be done, then power at low, mid, and high temporal frequencies will be used as covariates in the analyses of accommodative response. Other potential metrics might be lag-minutes or diopter-minutes, essentially area-under-the-curve summary measures of diopters of lag, or alternatively, diopters of accommodative response per minute of recording.

- vi. **Cycloplegic refractive error** will be measured at all visits. Refractive error will be measured by **cycloplegic retinoscopy** by a masked examiner (primary outcome of the treatment phase of the study). The parents of the subject will be instructed not to discuss the treatment group the patient is in to the masked examiner. Measurements will occur 30 minutes after drop instillation. One drop of proparacaine 0.5% will be instilled in each eye, followed by two drops of cycloplegic agents. The drops used for cycloplegia are the following:
 - 1. Tropicamide (1%) will be used only at the screening visit
 - 2. Cyclopentolate (1%) will be used during all remaining visitsThe neutral point for the horizontal meridian is recorded first, then the neutral point for the vertical meridian. If the axes are oblique, the true meridian is measured by projecting the retinoscopy beam on to a protractor on the wall. **SureSight autorefraction** will be also be performed on both eyes from 35cm by the investigator (unmasked).

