The basic analysis will be a two-sample t-test comparison of the change in refractive error between the two groups at 9 months and again at 18 months of age. Analysis of Covariance (ANCOVA) will be used to compare the change in refractive error between the two treatment groups adjusting for any possible confounding variables. Refractive error at 3 months along with any other identified confounders will be included as covariates in the analysis. Randomization of infants into the two treatment groups should protect against confounding, however, testing will be performed and adjustments made for imbalances in confounders between groups.

The relationship of accommodative effort and accommodative lag with change in refractive error between 3 and 9, or 3 and 18 months will be analyzed by repeated measures analysis of variance. We will fit a linear functions describing the relationship between change in refractive error and accommodation as the repeated factor, either effort or lag. A significant effect for type of accommodation will indicate that the greater slope is the better explanation of the driving force for change in refractive error.

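### The accommodation analysis names neither treatment arm nor 3-month refraction, so an arm effect can pass for an accommodation slope

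*Combined protocol and SAP*

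**What the plan says.** Section I (Objective) states the mechanism under test: "Our hypothesis is that more active and accurate accommodation, promoted with spectacle under-correction and accommodative exercises, will increase the rate of axial elongation" and so reduce hyperopia. The intervention is therefore expected to move accommodation and refraction together.

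Section F (Data Analysis) contains one accommodation analysis. It takes "The relationship of accommodative effort and accommodative lag with change in refractive error between 3 and 9, or 3 and 18 months" and fits linear functions by repeated measures analysis of variance, with type of accommodation (effort or lag) as the repeated factor. A significant effect of type is to mean that the steeper slope better explains what drives the refractive change. Treatment arm and 3-month refractive error are not named in this model. Three-month refraction is named as a covariate only in the separate ANCOVA that compares refractive change between arms.

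Section D.c.v (Accommodative response and lag) adds covariate rules. One is "Variability will be added as a covariate in analyses of the accommodative response". It goes on: "The simple standard deviation in accommodation is one measure of this variability". If Fourier analysis proves feasible, "then power at low, mid, and high temporal frequencies will be used as covariates in the analyses of accommodative response". No visit is given for any of these covariates. The schedule in section D.d records accommodation at baseline (V1) and at all six follow-up visits. Section D.c.v also qualifies the work: "There is no universally accepted outcome measure for infant accommodative response, therefore the analysis in this phase will be somewhat exploratory".

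**The concern.** If treatment shifts both the explanatory variable and the outcome, treated infants sit apart from controls on both axes. A line through the pooled data then has a slope even if, within each arm, infants who accommodate more show no greater loss of hyperopia. Section F would read that slope as evidence about the driver of refractive change.

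Three-month refraction raises a similar problem. Section II and Figure 1 present the change in hyperopia as a function of hyperopia at 3 months. Section D.c.v measures accommodation with no correction worn, so the demand on the infant also depends on the refractive error. Starting refraction can therefore influence both variables.

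What is at stake is the mechanistic claim that refraction changes by way of accommodation. The trial could report support for it when the data show only that the arms differ.

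The variability rule is a lesser matter. If the covariate is a follow-up value, taken from the same recording as the response, treatment may have altered it. An arm comparison of the response adjusted for it would not estimate the total treatment effect.

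**Working it through.** The plan gives no figure for this analysis, so there is none to reproduce.

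**Inputs from the plan** (sample-size paragraph before section C): difference between arms in refractive change 1.75 D; SD of change 1.50 D, taken as within-arm; 13 infants per arm; two-sided α = 0.05.

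**Assumptions**, because the documents give no accommodation data: treatment shifts accommodation by s = 0.4, 0.8 or 1.2 within-arm SD; there is no association between accommodation and refractive change within either arm; one value per infant; normal errors.

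**Expected pooled slope.** With equal arms, the between-arm covariance is 0.25 × s × 1.75 and the pooled variance of accommodation is 1 + 0.25s². The slope in D per SD of accommodation is

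0.4375s / (1 + 0.25s²)

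- s = 0.4: 0.175 / 1.04 = 0.17
- s = 0.8: 0.350 / 1.16 = 0.30
- s = 1.2: 0.525 / 1.36 = 0.39

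The true within-arm slope is zero in every case.

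**False-positive rate.** Simulated trials with these values, testing the slope against zero:

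| Shift in accommodation | Arms pooled (24 df) | Arm in model (23 df) |
|---|---|---|
| 0.4 SD | about 7–8% | 5% |
| 0.8 SD | about 15% | 5% |
| 1.2 SD | about 26–27% | 5% |

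The ranges reflect repeat simulations. With no shift (s = 0), the pooled test also stays at 5%.

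**Bearing on the plan's own test.** Section F compares the effort slope with the lag slope, not one slope with zero. The rates above therefore describe a single slope. The comparison is still exposed, because each pooled slope carries its own arm component. If treatment shifted effort by 0.8 SD and lag by 0.4 SD in the same direction, the pooled slopes would differ by 0.30 − 0.17 = 0.13 D per SD with no within-arm link for either. Shifts in opposite directions would give slopes of opposite sign.

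**Variability covariate.** Let treatment change the response by dA and variability by dV, and let their within-arm correlation be r, all in SD units. The arm effect adjusted for follow-up variability is dA − r × dV. Taking dA = 0.8 as an assumption:

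| dV | r | Adjusted effect | Change |
|---|---|---|---|
| 0 | any | 0.80 | none |
| −0.3 | −0.3 | 0.71 | 11% removed |
| −0.3 | −0.5 | 0.65 | 19% removed |
| −0.6 | −0.3 | 0.62 | 22.5% removed |
| −0.6 | −0.5 | 0.50 | 37.5% removed |
| −0.3 | +0.3 | 0.89 | 11% inflated |
| −0.6 | +0.3 | 0.98 | 22.5% inflated |

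A baseline value cannot carry a treatment effect, so adjusting for it removes none of the arm effect.

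**The case against.** The strongest defence is that the accommodation work is labelled somewhat exploratory. The primary outcome is masked cycloplegic retinoscopy, and its ANCOVA names neither accommodation nor variability. That stands and limits the consequence. It does not settle the matter, because accommodation is the mechanism in the study's stated hypothesis and section F gives its slope an explanatory reading.

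A second defence is that adding arm changes the question: the slope becomes a within-arm association, and precision is lost if arm accounts for much of the spread in accommodation. That is true and should be stated in the report. It is still the slope that bears on whether accommodation tracks refractive change beyond the arm difference.

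Third, section F is silent on these terms and does not exclude them, so the analyst might include them anyway. The planned adjustment for imbalances between groups, however, is attached to the arm comparisons of refractive change and does not extend to the accommodation model.

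A reader might infer more from the variability rule: that the plan adjusts for a post-randomisation variable and so removes part of the treatment effect. The documents do not support this. The visit is not stated, and a baseline recording exists. No between-arm test of the accommodative response is specified. Section I targets active and accurate accommodation, and steadiness is not the same thing. Section D.c.v also warns that inattention and drifting gaze disturb the readings, so variability may partly reflect recording quality.

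Nor do the documents say that unsteady infants will be dropped. The Fourier step is exploratory and conditional, and can be read as a single decision on whether to run it. What remains is that no rule covers the case where only some infants give usable 10-second segments.

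**Conclusion.** The concern holds for the accommodation model in section F. As written, it names neither treatment arm nor 3-month refraction, although the intervention is designed to move both accommodation and refraction. Under the plan's own refractive parameters, a single pooled slope would be falsely significant in about 7% to 27% of trials for accommodation shifts of 0.4 to 1.2 SD, against 5% with arm included. The shifts are assumed, and the calculation uses one value per infant with no within-arm link. The effect on the planned effort-versus-lag comparison has the same source, but its error rate has not been calculated. The contribution of 3-month refraction has not been quantified either.

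The variability rule needs clarification and cannot be called a demonstrated bias. Its visit and model are unspecified, and under assumed values the effect on an arm comparison runs from none, through removal of up to 37.5%, to inflation of up to 22.5%.

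The primary comparison of refractive change is not affected. The change should be made, but the trial's main result does not depend on it.

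**What to change.** In section F, add treatment arm and 3-month refractive error to the model relating accommodative effort and lag to refractive change, and state that the slopes are within-arm associations. Arm alone reduces the residual degrees of freedom with 26 infants from 24 to 23, in the one-value-per-infant simplification; adding 3-month refraction brings them to 22. Both variables are already collected.

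In section D.c.v, name the visit and the model for the variability covariate. If the accommodative response is compared between arms:

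- use only the V1 value as a covariate;
- analyse follow-up variability, and frequency power where obtainable, as separate outcomes by arm;
- keep infants without 10-second segments in the main accommodation analysis.

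These are wording changes and need no new measurement, since accommodation is scheduled at V1 and at every follow-up visit.

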A majority of the emmetropization process occurs within the first 18 months of life, particularly between 3 months and 9 months of age, leaving a small window of opportunity for potential intervention (Mayer et al., 2001; Mutti, Mitchell, Jones, et al., 2005). At 18 months of age, the mean refractive error in infants is $+1.10 \pm 0.90D$ (Mutti, Mitchell, Jones, et al., 2009). Once the infant phase of the emmetropization process is complete, residual significant levels of hyperopia can persist into childhood. If hyperopia is present past the age of emmetropization, it is unlikely the child will have the ability to “grow out of” their hyperopia (Jones, Mitchell, Mutti, et al., 2005). Failure to emmetropize leaves between 7.5% and 10% of school-aged children with clinically significant hyperopia ($> +2.00D$) (Kleinsteiner, Jones, Hullett, et al., 2003; Laatikainen and Erkkila, 1980).

Hyperopic children are more at risk for developing strabismus, specifically esotropia. Studies show a dose-dependent relationship between hyperopia and the risk of developing strabismus. Children than have a refractive error between +2.00D and +3.00D are 6.4 times more likely to develop an esotropia and those with a refractive error greater than +5.00 are 122 times more likely to develop esotropia (Cotter, Varma, Tarczy-Hornoch, et al., 2011). Anker et al. found that in children who developed esotropia, 18.4% were significantly hyperopic (+4.00D) and only 0.5% were emmetropic (Anker, Atkinson, Braddick, et al., 2004). Strabismus is a risk factor for the development of amblyopia, a decrease in visual acuity that creates impaired depth perception. Just as hyperopia shows a dose-response relationship with the development of strabismus, it shows a similar relationship with the development of amblyopia (Pascual, Huang, Maguire, et al., 2014).

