- iv. **Binocularity testing.** The examiner will determine if strabismus is present using a unilateral cover tests as well as Hirschberg evaluation. Subjects with an existing strabismus are not eligible. Subjects who develop a strabismus during the study period will be referred for further evaluation and retained for follow up.
- v. **Accommodative response and lag** will be measured with the Schaeffel PowerRefactor and by dynamic retinoscopy with no refractive correction worn.

The Schaeffel PowerRefactor is an infrared, binocular photorefractometer capable of measuring the meridional refractive error, and therefore the dynamic accommodative response, of both eyes simultaneously at 25 Hz. Photorefraction in general and this instrument specifically have been shown to compare well to conventional retinoscopic measures of accommodation with the added advantage of measuring accommodative response and its variability in both eyes over a more extended period of time (Blade and Candy, 2006; Braddick, Atkinson, French, et al., 1979; Howland, Dobson and Sayles, 1987; Rosenfield, Portello, Blustein, et al., 1996; Seidemann and Schaeffel, 2003). The PI's experience with this instrument is that maintaining attention is critical to the validity of measurements. Inattention and the drifting of gaze from central fixation on the accommodative target interfered with the comparability of measurements to conventional dynamic retinoscopy (Gabriel and Mutti, 2009). To filter out readings that might be obtained when fixation is poor, the "Gaze Control" setting on the PowerRefactor will be set to 15° in "Binocular" refraction mode.

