f. **Development of Strabismus.** The subject population of this study is at risk for developing strabismus (Anker et al., 2004; Cotter, 2007; Pascual et al., 2014). This will be discussed with the parents of potential subjects during screenings and during the consent process prior to the baseline examination. If a subject develops a strabismus, the subject will be discontinued from treatment in the study. The subject cannot remain in either arm of the study because of the different standard of care in prescribing philosophy that occurs with the development of strabismus (typically providing a full refractive correction for hyperopia). The subject will remain in the study and will continue to be followed for observation of all study measurements and outcomes. The subject's parents will have the option of their child remaining under the care of [name] in the Ohio State University College of Optometry Pediatric clinic, or any other doctor within the Ohio State University College of Optometry, or seek or be referred to another provider for a second opinion or for patient care. Any visits or treatment of strabismus or any clinical sequelae of the strabismus would be at the discretion of the licensed eye care provider and separate from the study. Follow up visits related to the study will follow the same schedule and contain the same measurements listed in the protocol.

E. **Internal Validity.** There are no threats to internal validity. All procedures performed in the examination are standard procedures that have been performed frequently in other studies. Threats to external validity might be present in selection bias. The sample of patients to be recruited will be identified at Riverside Pediatrics Associates by screenings of age appropriate infants. The screenings will be performed by [name], [name], or a nurse that has been adequately trained. The age, gender, and ethnicity of these patients might not be a true representation of the general population of full term, healthy infants.

F. **Data Analysis.** All data analysis will be performed using SPSS (Version 24). Statistical significance will be assessed using two-sided tests with an alpha level of 0.05. Data from both eyes will be included in all analyses and techniques to control for intra-subject correlations will be used.

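### The plan does not say in which arm, if any, an infant who develops strabismus is analysed, and read literally its wording leaves these infants out of the randomised comparison

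*Combined protocol and SAP*

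**What the plan says.** Section D.f (Development of Strabismus) makes three statements in sequence.

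- On treatment: "If a subject develops a strabismus, the subject will be discontinued from treatment in the study".
- On arm membership: "The subject cannot remain in either arm of the study because of the different standard of care in prescribing philosophy". The reason given is that care after strabismus typically means correcting the hyperopia in full.
- On follow-up: "The subject will remain in the study and will continue to be followed for observation of all study measurements and outcomes". The section closes by confirming that the visit schedule and measurements are unchanged.

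Section D.c.iv (Binocularity testing) covers the same event without mentioning arms: "Subjects who develop a strabismus during the study period will be referred for further evaluation and retained for follow up".

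Section F (Data Analysis) sets out the comparison, in a sentence that goes on to name 18 months as the second age: "The basic analysis will be a two-sample t-test comparison of the change in refractive error between the two groups at 9 months and again at". An ANCOVA of the same change follows. Its only statement on which data enter the analysis concerns eyes: "Data from both eyes will be included in all analyses and techniques to control for intra-subject correlations will be used". It defines no analysis population, has no intention-to-treat statement, and gives no rule for measurements taken after strabismus or after study treatment stops.

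**The concern.** An infant who belongs to neither arm has no place in a two-group t-test or ANCOVA, yet this infant's outcomes are collected to 18 months. The plan does not say what happens to those outcomes.

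The plan's own text suggests that the event is not a random loss:

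- Section II says: "Studies show a dose-dependent relationship between hyperopia and the risk of developing strabismus". It adds that "those with a refractive error greater than +5.00 are 122 times more likely to develop esotropia", and the randomised infants enter at +5.00D to +7.00D.
- Strabismus arises after randomisation, and whether spectacles are worn could plausibly affect it.
- Section D.f says the usual response is full correction. Section D.b.iii (Control group) says that infants given full correction, or 1.00D of under-correction, may fail to emmetropize.

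Leaving such infants out would condition the comparison on an event that may depend on both the treatment and the outcome. The protection given by randomisation would then be lost. With 15 infants per arm, each one is 6.7% of the arm. If the choice is left open, it can be made with the results in view, and either choice could be defended from the protocol.

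**Working it through.** **1. The passages side by side.** D.f says separately that treatment stops and that the infant cannot stay in either arm. It then says that the infant stays in the study. D.c.iv agrees with the last statement and is silent on arms. Section F neither excludes these infants nor assigns them to a group. Two readings therefore remain open: the infant leaves the regimen but is analysed in the randomised arm, or the infant leaves the arm and so the comparison.

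**2. The plan's own sample size.** Inputs from the sample-size paragraph before section C: difference 1.75D, SD of change 1.50D, two-sided alpha 0.05, beta 0.1, 13 per arm, 10% loss.

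- Simple two-mean formula: 2 x [1.50 x (1.960 + 1.282) / 1.75]^2 = 15.4, so 16 per arm.
- The plan attributes its 13 to repeated measurements but gives no correlation. If two measurements are averaged, the factor (1 + rho)/2 gives 13 for rho of about 0.55 to 0.68. The figure is attainable but cannot be verified. The present point does not depend on it.
- Loss: 13 / 0.90 = 14.4, so 15 per arm and 30 in total. This reproduces. The allowance is for infants who do not complete follow-up. It does not cover infants who complete and are then left out.

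**3. Bias if these infants are left out.** Count change as the reduction in hyperopia. Let q be the fraction of an arm removed, and let D be how much smaller the change is in the removed infants than in the rest. Removal raises that arm's mean by q x D, so the shift in treated minus control is (qT - qC) x D.

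The documents give neither q nor D, so both are assumed here: qT = 1/15, qC = 3/15, D = 1.0 to 2.0D.

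- D = 1.0: (0.067 - 0.200) x 1.0 = -0.13D; 0.13 / 1.75 = 8%.
- D = 2.0: (0.067 - 0.200) x 2.0 = -0.27D; 0.27 / 1.75 = 15%.

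With the counts swapped between arms, the shift is +0.13 to +0.27D. With equal counts and equal D, it is zero. A second assumed range, 1 to 3 of 13 removed from one arm only with D = 1.00 to 1.75D, moves that arm's mean by 0.08D (1/13 x 1.00) to 0.40D (3/13 x 1.75). That is 4% to 23% of 1.75D.

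**4. Power for the same scenario.** Two-sample t-test, difference 1.75D, SD 1.50D, no repeated-measures gain (noncentral t):

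| Infants analysed | Power |
|---|---|
| 15 v 15 | 86.9% |
| 14 v 12 (1 treated and 3 controls left out) | 81.2% |
| 13 v 13 (two per arm lost to follow-up) | 81.4% |
| 12 v 10 (both) | 73.6% |

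If the plan's 90% at 13 per arm is granted, the effective SD is 1.50 x sqrt(13 / 15.44) = 1.38D. On the normal approximation:

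- 15 v 15: 1.75 / (1.376 x sqrt(1/15 + 1/15)) = 3.48, and Phi(3.48 - 1.96) = 93.6%.
- 14 v 12: 1.75 / (1.376 x sqrt(1/14 + 1/12)) = 3.23, and Phi(3.23 - 1.96) = 89.8%.

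On that basis the loss is about 4 percentage points.

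**The case against.** A reader might infer that the protocol definitely removes these infants from the analysis. The documents do not support that. The sentence is in the clinical procedures, directly after the statement that treatment stops, and its stated reason is about prescribing. It can be read as saying that neither regimen, under-correction or observation, can continue. Control infants have no study spectacles to stop, so some such sentence is needed to explain why observation also ends. No sentence in the available text excludes these infants from the t-test or ANCOVA, and collecting every outcome fits inclusion at least as well as exclusion. Section F also says that randomisation into the two groups should protect against confounding, which points towards analysis by allocation.

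A reader might also infer that the bias favours the spectacles, or that the 122-fold figure implies many events. Neither follows. The figure is a relative risk in children and gives no incidence by 18 months. The direction of bias depends on how events split between arms, which is not given. Section II ties strabismus to the level of hyperopia, whereas the outcome is change, and the ANCOVA adjusts for the 3-month value. A smaller change in strabismic infants is plausible but not documented.

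These objections remove any claim of certain exclusion or of a known size. They do not settle the ambiguity. The statement about arms is separate from the statement about treatment, the remark about randomisation does not define an analysis population, and baseline adjustment cannot restore infants who are not in the data set.

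**Conclusion.** The point holds as an ambiguity that should be closed before analysis. The plan takes strabismic infants out of both arms, keeps measuring them, and does not say where they are analysed. Exclusion is the literal reading, and discretion after seeing the data is the best case.

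The shift of -0.13 to -0.27D, and the fall in simple t-test power from 86.9% to 81.2%, are illustrations. They rest on an assumed incidence, an assumed split between arms and an assumed D. The power figures also leave out the repeated-measures gain that the plan claims. Bias and analyst discretion matter more than the loss of power. If no infant develops strabismus, nothing is lost.

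The text between the Background and the eligibility list was not available for this check. It should be searched for a statement on the analysis population.

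**What to change.** 1. In D.f, replace the wording on arms with: the infant stops the assigned study regimen but stays in the randomised arm for analysis. Align D.c.iv with it.
2. In section F, state that all randomised infants are analysed in the arm assigned, using all 9- and 18-month measurements, including those taken after strabismus and any change of correction.
3. Report the number of infants with strabismus by arm.
4. Add a sensitivity analysis that uses only data before onset. An infant with onset before 9 months would add nothing to a t-test of 9- or 18-month change, so this analysis is better run as a repeated-measures model over all scheduled visits, with its missing-data assumption stated.

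The cost is a few sentences, because the outcomes are already collected. The small downside is that the primary estimate then reflects a treatment policy that includes any correction prescribed later, which may itself affect emmetropization. The sensitivity analysis shows how much this matters. The clinical care rules stay as they are.
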